### 9.3 Other Efficacy and Safety Analyses

#### 9.3.1 Binary Outcomes

Subjects with an event will be listed for the following outcomes:

- any one of the primary endpoint components within 60 days post randomization
- CV mortality at 28 days post randomization

#### 9.3.2 Columbia Suicide Severity Rating Scale (C-SSRS)

To monitor for the emergence of suicidal ideation and behavior, subjects will undergo C-SSRS evaluations at baseline and at Day 28.

The number of subjects experiencing suicidal Ideation or suicidal behavior will be summarized. Shift tables in relation to suicidal ideation and/or behavior from baseline to

Day 28 will be presented.

There will be no imputation of missing data for C-SSRS.

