9.2.9 Suicide Severity Rating Scale (C-SSRS)

The C-SSRS is a questionnaire designed for the assessment of suicidal ideation and behavior in adolescents and adults.

To monitor for the emergence of suicidal ideation and behavior, subjects will undergo C-SSRS evaluations at baseline and at Day 28.

The questionnaire must be administered by an investigator or other individual that is suitably qualified by education or training. See Appendix 17.4 for a sample C-SSRS – Baseline/Screening version assessment and Appendix 17.5 for a sample 28-day post-dose C-SSRS assessment.

If there is a positive result for suicidality on the C-SSRS after screening (defined by a subject answering 'yes' to questions 4 or 5 on the suicidal ideation portion of the C-SSRS), the subject will be evaluated by an investigator or medically qualified sub-investigator for continuation in the study.

If a subject becomes suicidal during the study, an investigator or medically qualified sub-investigator should provide the appropriate treatment to the subject.

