17.3 Patient Impression of Change Questionnaire

Since the start of this study, my overall status is:

✓ one box only:

Much Improved

Improved

No Change

Worse

Much Worse

PROPRIETARY AND CONFIDENTIAL

**17.4 COLUMBIA-SUICIDE SEVERITY RATING SCALE (C-SSRS) –
BASELINE/SCREENING VERSION**

**COLUMBIA-SUICIDE SEVERITY
RATING SCALE
(C-SSRS)**

Baseline/Screening Version
Version 1/14/09

***Posner, K.; Brent, D.; Lucas, C.; Gould, M.; Stanley, B.; Brown, G.;
Fisher, P.; Zelazny, J.; Burke, A.; Oquendo, M.; Mann, J.***

Disclaimer:

This scale is intended to be used by individuals who have received training in its administration. The questions contained in the Columbia-Suicide Severity Rating Scale are suggested probes. Ultimately, the determination of the presence of suicidal ideation or behavior depends on the judgment of the individual administering the scale.

Definitions of behavioral suicidal events in this scale are based on those used in The Columbia Suicide History Form, developed by [name] and [name], Conte Center for the Neuroscience of Mental Disorders (CCNMD), New York State Psychiatric Institute, [name]. (Oquendo M. A., Halberstam B. & Mann J. J., Risk factors for suicidal behavior: utility and limitations of research instruments. In M.B. First [Ed.] Standardized Evaluation in Clinical Practice, pp. 103 -130, 2003.)

For reprints of the C-SSRS contact [name]., New York State Psychiatric Institute, [name]; inquiries and training requirements contact [contact]

© 2008 The Research Foundation for Mental Hygiene, Inc.

PROPRIETARY AND CONFIDENTIAL

PART 1 OF 5

SUICIDAL IDEATION		Lifetime: Time He/She Felt Most Suicidal	Past ___ Months

Ask questions 1 and 2. If both are negative, proceed to "Suicidal Behavior" section. If the answer to question 2 is "yes", ask questions 3, 4 and 5. If the answer to question 1 and/or 2 is "yes", complete "Intensity of Ideation" section below.
 
1. Wish to be Dead Subject endorses thoughts about a wish to be dead or not alive anymore, or wish to fall asleep and not wake up. Have you wished you were dead or wished you could go to sleep and not wake up?
 
If yes, describe:
		Yes  No 	Yes  No 

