Suicidal Behavior: Suicidal behavior was present during the assessment period?	Yes  No 	Yes  No 
--	--	--

PROPRIETARY AND CONFIDENTIAL

PART 5 OF 5

 Section below not applicable			
Answer for Actual Attempts Only	Most Recent Attempt Date: _____	Most Lethal Attempt Date: _____	Initial/First Attempt Date: _____
Actual Lethality/Medical Damage: 0. No physical damage or very minor physical damage (e.g., surface scratches). 1. Minor physical damage (e.g., lethargic speech; first-degree burns; mild bleeding; sprains). 2. Moderate physical damage; medical attention needed (e.g., conscious but sleepy, somewhat responsive; second-degree burns; bleeding of major vessel). 3. Moderately severe physical damage; medical hospitalization and likely intensive care required (e.g., comatose with reflexes intact; third-degree burns less than 20% of body; extensive blood loss but can recover; major fractures). 4. Severe physical damage; medical hospitalization with intensive care required (e.g., comatose without reflexes; third-degree burns over 20% of body; extensive blood loss with unstable vital signs; major damage to a vital area). 5. Death	Enter Code _____	Enter Code _____	Enter Code _____
Potential Lethality: Only Answer if Actual Lethality=0 Likely lethality of actual attempt if no medical damage (the following examples, while having no actual medical damage, had potential for very serious lethality: put gun in mouth and pulled the trigger but gun fails to fire so no medical damage; laying on train tracks with oncoming train but pulled away before run over).	Enter Code _____	Enter Code _____	Enter Code _____
0 = Behavior not likely to result in injury 1 = Behavior likely to result in injury but not likely to cause death 2 = Behavior likely to result in death despite available medical care			

PROPRIETARY AND CONFIDENTIAL

**17.5 COLUMBIA-SUICIDE SEVERITY RATING SCALE (C-SSRS) –
SINCE LAST VISIT VERSION**

**COLUMBIA-SUICIDE SEVERITY
RATING SCALE
(C-SSRS)**

Since Last Visit
Version 1/14/09

**Posner, K.; Brent, D.; Lucas, C.; Gould, M.; Stanley, B.; Brown, G.;
Fisher, P.; Zelazny, J.; Burke, A.; Oquendo, M.; Mann, J.**

Disclaimer:

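### The C-SSRS shift table in SAP 9.3.2 compares forms with different look-back periods: unmatchable for behavior, and for ideation dependent on which baseline column is used

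*SAP*

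**What the plan says.** SAP 9.3.2 gives the purpose of the assessment as "To monitor for the emergence of suicidal ideation and behavior", and states that "subjects will undergo C-SSRS evaluations at baseline and at Day 28". It plans two summaries. One is a count: "The number of subjects experiencing suicidal Ideation or suicidal behavior will be summarized". The other is a set of tables: "Shift tables in relation to suicidal ideation and/or behavior from baseline to" Day 28. Neither SAP 9.3.2 nor the general baseline definition in SAP 6.6.3 (the last record before first dose) says which look-back column supplies the baseline status, or which categories are shifted.

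Protocol 9.2.9 assigns a different form to each time point: "See Appendix 17.4 for a sample C-SSRS – Baseline/Screening version assessment", and "Appendix 17.5 for a sample 28-day post-dose C-SSRS assessment". The ideation page in Appendix 17.4 has one column headed "Lifetime: Time He/She Felt Most Suicidal" and a second for a recent number of months, left blank. Its behavior pages have a lifetime column and one for a recent number of years, also blank. Appendix 17.5 is titled "SINCE LAST VISIT VERSION" and has no other period.

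Change in C-SSRS is a secondary safety endpoint (SAP 4.2.2). It is summarized descriptively, without a test (SAP 6.2 and 6.4).

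**The concern.** A shift table reads as change only if both margins measure the same thing over comparable periods. Here the baseline margin may cover decades and the Day 28 margin covers at most about four weeks. A patient whose only positive answer concerns the distant past then moves from yes to no without having changed. A patient with such a history who becomes suicidal on study treatment lands in the yes-to-yes cell and reads as unchanged.

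The section exists to detect emergence, and that second patient is one it is meant to find. Because no test is planned, these tables are the evidence for the endpoint. SAP 6.6.3 does not settle the question, because both look-back columns belong to the same pre-dose record.

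**Working it through.** The plan states no figure on this point, so there is nothing to reproduce. The check has two parts.

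**1. Look-back periods side by side**

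| Domain | Baseline form (17.4) | Day 28 form (17.5) | Can they match? |
|---|---|---|---|
| Ideation | Lifetime, or past months (number blank) | Since last visit | Lifetime: no. Months: only if the period recorded was about one month |
| Behavior | Lifetime, or past years (number blank) | Since last visit | No, with either column |

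The C-SSRS is given only at baseline and Day 28, but Protocol Appendix 17.2.1 has a visit on Day 21. The Day 28 form therefore covers about 28 − 21 = 7 days if read literally, or about 28 days if it is taken to mean since the baseline C-SSRS. A column counted in years exceeds both. A single combined ideation-and/or-behavior status inherits the behavior mismatch.

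**2. What the mismatch does when nothing changes**

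The documents give no rates, so all inputs here are assumptions:

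- L: share of enrolled patients positive on the lifetime column.
- h: probability of a positive answer over 28 days in those patients.
- r: the same probability in patients without such a history, set at 0.5%.

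Both probabilities are the same before and after baseline, and the two periods are independent.

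Expected cells per 100 patients with a lifetime baseline:

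- yes to no = 100 × L(1 − h)
- no to yes = 100 × (1 − L)r
- yes to yes = 100 × Lh

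With a baseline period matched to 28 days, each direction is 100 × [Lh(1 − h) + (1 − L)r(1 − r)].

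For L = 10% and h = 10%:

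- yes to no = 100 × 0.10 × 0.90 = 9.0
- no to yes = 100 × 0.90 × 0.005 = 0.45
- yes to yes = 100 × 0.10 × 0.10 = 1.0
- share of Day 28 positives in the unchanged cell = 1.0 / 1.45 = 69%
- matched = 100 × (0.10 × 0.10 × 0.90 + 0.90 × 0.005 × 0.995) = 1.35 each way

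| L | h | Yes to no | No to yes | Yes to yes | Share of Day 28 positives unchanged | Matched, each way |
|---|---|---|---|---|---|---|
| 0 | any | 0 | 0.50 | 0 | 0% | 0.50 |
| 2% | 5% | 1.9 | 0.49 | 0.1 | 17% | 0.58 |
| 2% | 50% | 1.0 | 0.49 | 1.0 | 67% | 0.99 |
| 10% | 10% | 9.0 | 0.45 | 1.0 | 69% | 1.35 |
| 20% | 5% | 19.0 | 0.40 | 1.0 | 71% | 1.35 |
| 20% | 50% | 10.0 | 0.40 | 10.0 | 96% | 5.40 |

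With a lifetime baseline and any positive L in this range, apparent improvement exceeds apparent worsening although nothing has changed. With matched periods the two are equal. With L = 0 the distortion vanishes.

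**The case against.** The strongest reply is that SAP 9.3.2 never says it uses the lifetime column. For ideation an analyst could take the recent-months column, and the blank is on a form that the protocol calls a sample, so the form used at sites may have carried a short period. This stands for ideation. It does not help behavior, where both columns are longer than the Day 28 period.

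Second, exclusion 23 removes patients who show suicidal tendency on the screening C-SSRS. If it were applied to lifetime answers, there would be no baseline positives and no distortion. That is possible. The criterion names no item and no look-back period, so a remote history is neither clearly barred nor clearly allowed.

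Third, a reader might infer that the table shows improvement by construction and conceals emergent cases. The documents do not support that. The lean depends on the column used and on who was enrolled. A recurrent case stays in the Day 28 yes margin, which comes only from the Day 28 form. Events that meet the adverse event definition are tabulated under SAP 9.3.8, and Protocol 9.2.9 requires individual evaluation of certain positive answers after screening. The separate count in SAP 9.3.2 may also show such cases, but it states no period and could include baseline history.

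Fourth, both arms complete the same forms, so the randomized comparison of Day 28 positives is not biased. This stands: the difficulty lies in reading shifts within an arm and in identifying emergent cases.

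Fifth, scaling the illustration to the planned 211 per arm would mislead, because SAP section 2 says the trial was terminated early and the SAP does not give the number enrolled. The results above are therefore per 100 patients only.

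**Conclusion.** The point holds as a mismatch that the SAP leaves unaddressed. It is certain for behavior. For ideation it is certain if the lifetime column is used and otherwise depends on the recent period recorded. If patients with a past history were enrolled, the within-arm shift leans toward improvement and on-treatment cases among them are classed as unchanged, though not lost from the Day 28 margin.

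The size runs from nil (no past positives enrolled) upward and cannot be set from the documents. The figure of 9.0 against 0.45 per 100 shows the mechanism under assumed rates and is not an estimate for this trial. The conclusion rests on the text of SAP 9.3.2 and 6.6.3 and on the sample forms. If table shells or the completed forms fix the column and period, that choice should be stated in 9.3.2.

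**What to change.** Revise SAP 9.3.2 before the blind is broken, which SAP section 2 allows because the plan is to be approved before then:

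- Report lifetime ideation and lifetime behavior as baseline characteristics only.
- Add a by-arm table of the number and percent of patients with any ideation or behavior on the Day 28 form, for all patients and split by baseline history.
- Present ideation and behavior separately. For the ideation shift, use the recent-period column as baseline, by severity category, with a footnote giving the period recorded at baseline and the period the Day 28 form was taken to cover.
- State that the behavior shift is not interpreted as change, because its look-back periods cannot be matched.

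The cost is one extra descriptive table and a footnote, with no new data. Filling in the blanks on the form now would not help, since it cannot alter answers already collected. If sites recorded different recent periods, the footnote has to say so and the ideation shift remains only partly comparable.

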### **9.3.3 Patient Impression of Change Questionnaire (PICQ)**

The patient will be asked to document how her/his overall status changed.

Data will be listed.

### **9.3.4 Laboratory Tests**

For laboratory (Local Laboratory) data both scheduled and unscheduled post-baseline values will be tabulated. Descriptive statistics of the observed values and change from baseline (continuous data) will be presented by treatment group and visit for each parameter.

Each measurement (continuous data) will be classed as low(below normal range), normal (within normal range), or high (above normal range), based on ranges supplied by the laboratory used. Shift tables in relation to the normal range from baseline to each post Baseline visit will be presented.

As normal range for these assays may depend on gender, when applicable, data will be tabulated separately for men and women when applicable.

Additionally, a summary of targeted parameters against specified threshold limits will be presented.

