If, following initiation of the investigational product, it is subsequently discovered that a study patient is pregnant or may have been pregnant at the time of investigational product exposure, including during at least 6 half-lives (18 days) after product administration, the investigational product will be permanently discontinued and the pregnancy will be reported to the Sponsor and the Contract Research Organization (CRO) within 24 hours of the site's awareness of the event. Worldwide Clinical Trials (WWCT) has been contracted as the CRO for this trial. Protocol-required procedures for study discontinuation and follow-up must be performed on the patient unless contraindicated by pregnancy. Other appropriate pregnancy follow-up procedures should be considered if indicated.

9.2.14.3 *Drug-Induced Liver Injury (DILI)*

Wherever possible, timely confirmation of initial liver-related laboratory abnormalities should occur prior to the reporting of a potential DILI event. All occurrences of potential DILIs, meeting the defined criteria below, must be reported as SAEs.

Potential DILI is defined as:

1. ALT or AST elevation $> 8 \times \text{ULN}$

OR
2. ALT or AST elevation $> 5 \times \text{ULN}$ for more than 2 weeks

OR

3. ALT or AST elevation $> 3 \times \text{ULN}$ and bilirubin $> 2 \times \text{ULN}$ or INR > 1.5 .

If a patient meets one of the above criteria, the study drug needs to be discontinued and the assessments of ALT, AST, bilirubin and alkaline phosphatase, as well as a physical examination need to be repeated every 24 hours until all abnormalities have normalized (in the investigator's opinion) or returned to the baseline state.

Elevations in ALT or AST $> 3 \times \text{ULN}$ or bilirubin $> 2 \times \text{ULN}$ alone, i.e., when not concomitant, are not grounds for withdrawal but are to be followed up, as above, within 72 hours of notice of abnormal results.

9.2.14.4 *Overdose*

All occurrences of overdose must be reported as SAEs. An overdose is defined as the accidental or intentional administration of any dose of a product that is considered both excessive and medically important.

9.2.14.5 *Drug-Drug Interactions*

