### **6.5 *Handling of Unscheduled Visits***

Visit data will be presented using nominal times as collected in the eCRF. Both scheduled and unscheduled post-baseline visits will be tabulated. Unscheduled visits will be presented as 'Visit.x.xx' (e.g. Visit 3.01).

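### Laboratory shift tables run visit by visit and unscheduled draws get rows of their own, so for liver tests some rows hold patients selected by an abnormal result, and no stated shift table counts patients who ever went out of range

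*SAP*

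**What the plan says.** SAP 6.5 covers visit data in general: "Both scheduled and unscheduled post-baseline visits will be tabulated". Each unscheduled visit keeps its own label, such as Visit 3.01, and is not merged into a scheduled time point.

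SAP 9.3.4 repeats this for the local laboratory: "both scheduled and unscheduled post-baseline values will be tabulated". Descriptive statistics "will be presented by treatment group and visit for each parameter". Each value is classed low, normal or high against the ranges of the laboratory that measured it, and then: "Shift tables in relation to the normal range from baseline to each post Baseline visit will be presented". Because some ranges may depend on sex, "data will be tabulated separately for men and women when applicable". One further output is promised: "Additionally, a summary of targeted parameters against specified threshold limits will be presented". The text does not give its parameters, its limits, or whether it counts per visit or at any time.

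Laboratory changes over 28 days, including ALT, AST, bilirubin, eGFR, creatinine, INR and lymphocyte count, are secondary safety endpoints (Protocol 4.2.3, SAP 4.2.2). Protocol 9.1 schedules post-baseline local laboratory tests on Days 7, 14 and 28.

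Protocol 9.2.14.3 says that, once a criterion for potential drug-induced liver injury is met, ALT, AST, bilirubin and alkaline phosphatase "need to be repeated every 24 hours until all abnormalities have normalized" or returned to the baseline state. Isolated lesser elevations of transaminases or bilirubin are followed up within 72 hours.

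**The concern.** Two things follow from reading these sections together.

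First, for the liver tests the protocol itself generates unscheduled draws, and it does so because a result was abnormal. A row for an unscheduled visit then sets the arms side by side within a subset defined by a post-randomisation outcome, at differing study days. One patient with daily repeats can fill several such rows. These rows are not randomised comparisons, although they appear in the same tables as rows that are.

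Second, a by-visit shift table reports how many patients were out of range at that visit. For safety the reader also wants to know how many patients in each arm were ever out of range. By-visit tables do not determine that number. A rise between scheduled visits would appear only in an unscheduled row and would not be carried into any per-patient shift over the treatment period.

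**Working it through.** The plan states no figure on this point, so there is none to reproduce. The check has three parts.

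**1. What by-visit rates say about the share ever abnormal.** Inputs: three scheduled post-baseline visits (Protocol 9.1) and a rate *p* newly high at each. The documents give no *p*; the values below are assumptions. With the same patients at each visit, the share ever high at those visits lies between max(*p*₁, *p*₂, *p*₃), when the same patients are high each time, and min(1, *p*₁ + *p*₂ + *p*₃), when they are different patients. If visits were independent it would be 1 − (1 − *p*)³.

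| Assumed rate per visit | Lowest share ever high | If independent | Highest share ever high |
|---|---|---|---|
| 5% | 5% | 1 − 0.95³ = 14.3% | 15% |
| 10% | 10% | 1 − 0.90³ = 27.1% | 30% |
| 20% | 20% | 1 − 0.80³ = 48.8% | 60% |

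At the planned 211 per arm, the 5% line covers 0.05 × 211 ≈ 11 to 0.15 × 211 ≈ 32 patients ever high. Two arms with identical by-visit tables could sit at opposite ends of that range. Unscheduled results can only add to the count.

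**2. How large an unscheduled row might be.** The documents give neither the number enrolled at early termination nor the rate of unscheduled draws. Assume that 2% to 10% of an arm has a given unscheduled visit. The row then holds 0.02 × 211 ≈ 4 to 0.10 × 211 ≈ 21 patients per arm at full enrolment, or 1 to 5 at an assumed 50 per arm. SAP 6.2.3 bases percentages on the column-header count unless footnoted. A row of four patients, all high, could therefore read as 4/211 = 1.9% of the arm or 4/4 = 100% of the row.

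**3. What the SAP does elsewhere.** SAP 9.2 leaves unscheduled and repeat measurements out of the area-under-the-curve calculation and defines a maximum post-baseline change to Day 28 for the central-laboratory markers. SAP 9.3.8 tabulates each patient's maximum adverse event severity. The per-patient extreme is thus already used in two places, but the text gives no such rule for local laboratory shifts.

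**The case against.** The best reply is that the consequences are limited and partly covered elsewhere.

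- **Other routes to a patient-level count.** The threshold summary in SAP 9.3.4 may well count patients at any time. Abnormal laboratory findings can be reported as adverse events, potential drug-induced liver injury must be reported as serious, and SAP 9.3.8 counts each patient once per preferred term. This stands: a reader who infers that transient abnormalities are counted nowhere goes further than the documents allow. It does not close the gap, because the threshold summary's time basis is unstated and event coding does not replace a shift against the normal range for every parameter.
- **Selection.** A reader might infer that every unscheduled laboratory row is selected by an abnormal result. The protocol shows this only for the liver tests. Unscheduled blood counts or creatinine may have other reasons.
- **Sex split.** A reader might infer that splitting by sex removes the overall comparison of arms or costs precision. The split applies only when applicable, the SAP does not say that pooled tables are dropped, and no confidence interval is planned for laboratory shifts.
- **Understated incidence.** By-visit tables do not understate incidence. They report status at each visit and claim nothing more.
- **No test is affected.** Laboratory summaries are descriptive in an abbreviated report (SAP 2, 6.2, 6.4). This stands, and it is why the point is minor.
- **The worst value depends on testing frequency.** Patients who are retested have more chances of an extreme result. This stands and should be stated with the table.

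The point concerns the SAP's text. Table shells, if they exist, might already supply a worst-value shift.

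**Conclusion.** The point holds as a modest improvement to safety reporting. As written, the SAP gives unscheduled laboratory visits their own rows, which for liver tests are largely outcome-selected, and it defines shifts only to each visit. The share of each arm that ever left the normal range is therefore not given by any stated shift table. Under an assumed 5% at each of three visits, that share is left undetermined between 5% and 15%. The ambiguity follows from the layout; its size depends on the assumed rate. The row sizes likewise rest on assumed retest rates and arm sizes. No error rate, test or stated figure changes.

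**What to change.** Amend SAP 6.5 and 9.3.4 as follows.

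1. Restrict by-visit laboratory summaries and by-visit shift tables to scheduled visits, and list unscheduled values.
2. Add one shift table per parameter from baseline to the worst post-baseline value through Day 28, over all scheduled and unscheduled results. Use the highest value for ALT, AST, alkaline phosphatase, bilirubin, creatinine, INR and LDH, and the lowest for hemoglobin, leukocytes, lymphocytes, platelets and eGFR.
3. Class each value by its applicable sex-specific range, then show men and women pooled.
4. Footnote that the worst value depends partly on how often a patient was tested.

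It would also help to state the parameters, limits and time basis of the threshold summary. No new data are needed. The cost is SAP wording and a few more tables, offset in part by dropping the sparse unscheduled rows.
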